## Division & Personnel

### Division

What Division/Department does the PI belong to?

SUBSTANCE USE

Within the division/department, what Center or group are you affiliated with, if any?

SUBSTANCE TREATMENT AND RESEARCH SERVICES

### Unaffiliated Personnel

List investigators, if any, who will be participating in this protocol but are not affiliated with New York State Psychiatric Institute or Columbia University. Provide: Full Name, Degrees and Affiliation.

none

## Procedures

To create the protocol summary form, first indicate if this research will include any of the following procedures

- ✓ Psychiatric Assessment
- ✓ Medication Trial
- ✓ Use of Placebo or Sham Treatment
- ✓ Off-label Use of Drug or Device

## Population

Indicate which of the following populations will be included in this research

- ✓ Medically and Psychiatrically Healthy Subjects
- ✓ Adults
- ✓ Adults over 50
- ✓ Substance Users

## Research Support/Funding

Will an existing internal account be used to support the project?

Yes

Describe internal account

U54DA037842-01 Shared Pharmacotherapeutic Strategies for Cannabinoid & Opioid Use Disorders

Is the project externally funded or is external funding planned?

Yes

Select the number of external sources of funding that will be applicable to this study

## Funding Source #1

Is the PI of the grant/contract the same as the PI of the IRB protocol?

No

Who is the PI of the grant/contract?

[name], MD

Select one of the following

The grant/contract is currently funded

Source of Funding

Federal

Institute/Agency

NIDA

Grant Name

Shared Pharmacotherapeutic Strategies for Cannabinoid & Opioid Use Disorders

Grant Number

U54DA037842-01

Select one of the following

Single Site

Business Office

RFMH

Does the grant/contract involve a subcontract?

Yes

Subcontracted?

To

Name institution(s)

Columbia University

## Study Location

Indicate if the research is/will be conducted at any of the following

Other Columbia University Medical Center Facilities

This protocol describes research conducted by the PI at other facilities/locations

No

## Lay Summary of Proposed Research

Lay Summary of Proposed Research

We propose to recruit patients with **Opioid Use Disorder (OUD)** seeking treatment into our program of outpatient detoxification and naltrexone induction followed by a relapse-prevention treatment with **Extended release-naltrexone (XR-NTX)**. Eligible participants will be randomly assigned to adjunctive treatment with lorcaserin (N = 40), or placebo (N = 20) with weekly therapy. Lorcaserin **or placebo** 10 mg bid will be started on Day 1 of the study to address acute withdrawal, then maintained over the next 5 weeks, and stopped after the second XR-naltrexone is administered. Patients will be seen twice weekly for monitoring and offered two injections of naltrexone; at the end of oral naltrexone induction (end of week 1) and four weeks later (week 5). The primary outcome measure will be the proportion of patients successfully retained to receive the second naltrexone injection. Patients retained to this point tend to stay on treatment and do well long term, hence this is the most clinically relevant outcome to evaluate treatment initiation.

## Background, Significance and Rationale

Background, Significance and Rationale

Opioid Use Disorder (OUD) has reached epidemic proportions in the US with more than 2.5 million individuals affected, and substantial morbidity, including fatal overdose, now a leading cause of accidental death. Ironically, while opioid dependence is among the most severe addictions, it also has the most effective medication treatments. Yet, most patients with OUD are not engaged in any form of treatment and those in treatment do not continue with the medication for a sufficient period of time to assure sustained abstinence. The immediate goal of this proposal is to help improve the acceptability and effectiveness of the new treatment strategy, opioid withdrawal followed by a relapse prevention using extended-release injectable formulation of naltrexone (XR-naltrexone), in order to ultimately expand the availability of effective treatment options for opioid dependence.

The recent advent of XR-naltrexone has improved adherence to naltrexone and approximately 50% of patients started on injectable naltrexone are successful in treatment at 6 months, comparable with outcome of buprenorphine-assisted treatment but with lower rates of continuing opioid use. However, in order to safely initiate treatment with XR-naltrexone, an opioid dependent patient needs to undergo opioid withdrawal (detoxification) and be rapidly inducted onto the medication, which involves additional withdrawal discomfort. We developed an outpatient detoxification and naltrexone induction procedure, which has high patient acceptability and success rates, but the problems of withdrawal discomfort, persistent craving, and resulting dropout before the first XR-naltrexone dose persist. We have also shown that in addition to acute opioid withdrawal during the induction, subacute withdrawal symptoms, craving, and insomnia persist during the first several weeks after the first XR-naltrexone dose and may contribute to early dropout (after 1-2 injections). Thus, withdrawal discomfort and persistent craving is a likely common element underlying both failure of induction and early attrition from naltrexone treatment.

We are pursuing a program of research to develop pharmacological strategies that will increase success of induction and increase retention on XR-naltrexone. Here, we propose to conduct a pilot trial to test lorcaserin, a 5HT2c receptor (5HT2cR) agonists which recently become available for clinical use. Variety of 5HT2cR agonists, including lorcaserin, were found to be effective in preclinical models predictive of their efficacy in treatment of neuropsychiatric disorders including effects on mood, anxiety, impulsivity, learning and memory, psychosis, and food intake. Recently emerging area of research include studies indicating that 5HT2cR agonists may be effective in treatment of substance use disorders as these agents were found to: decrease self-administration of drugs of abuse, reduce reinstatement of drug-seeking behavior induced by stress as well as pharmacological and environmental cues, reduce motivational aspects of drug withdrawal, and reduce impulsive responding. Recent data suggest effectiveness of lorcaserin in alleviating opioid withdrawal (**Gobert et al., 2000; Wu et al., 2015; Zang et al., 2016**). Encouraging findings from preclinical models was confirmed by the recent positive results of the smoking cessation clinical trial (**Shanahan et al., 2016**). Consequently, there is strong support to suggest a first, proof-of-concept clinical trial of lorcaserin as a treatment of OUD and studying its potential to improve relapse-prevention effects of XR-naltrexone seems to be most fitting with the available evidence.

## Specific Aims and Hypotheses

## Specific Aims and Hypotheses

Specific Aim #1: To determine whether lorcaserin, compared to placebo, increases the proportion of patients successfully inducted onto injectable naltrexone and retained to receive the second monthly injection.

Specific Aim #2: To determine whether lorcaserin, compared to placebo, reduces severity of acute withdrawal and craving during detoxification and induction prior to the first injection and protracted withdrawal after the first injection.

This will be the first clinical trial of lorcaserin for treatment of opioid withdrawal and the facilitation of naltrexone induction. If found effective, adjunctive lorcaserin would be a significant advance in the initiation of treatment with XR-naltrexone. As such, this method would have the potential to expand the population of individuals with OUD for whom naltrexone is a viable treatment option.

## Description of Subject Population

### Sample #1

Specify subject population

Adults ages 18-60 with current Opioid Use Disorder

Number of completers required to accomplish study aims

40

Projected number of subjects who will be enrolled to obtain required number of completers

60

Age range of subject population

18-60

Gender, Racial and Ethnic Breakdown

Both males and females will be recruited. All eligible subjects are accepted; however, past experience with recruitment for other studies in this population suggests that that the sample will be 75% male, 60% Caucasian, 30% Hispanic or Latino, and 10% Black or African-American.

Description of subject population

Adults ages 18-60 with current Opioid Use Disorder.

## Recruitment Procedures

Describe settings where recruitment will occur

All potential participants will be evaluated at the Substance Treatment and Research Service (STARS) clinic at the New York State Psychiatric Institute.

How and by whom will subjects be approached and/or recruited?

All patients will be seen by one of our psychiatrists or psychologists for a screening

evaluation and mental status examination as part of routine admission procedures at STARS (Evaluation of Potential Substance Abuse Participants, IRB # 6582R, PI: [name]). Patients who are opiate dependent and appear to meet criteria are told about the study and offered further evaluation. Final informed consent for the study will be obtained after full psychiatric and medical workup is complete. The physicians listed above work regular weekly shifts at STARS, know the protocol well, and are able to explain study consent to the participant. Procedures for training staff physicians in each protocol and consent form include initial presentations by the Principal Investigator at weekly staff meetings, and weekly discussion of inclusion/exclusion criteria and study eligibility for each screening participant.

How will the study be advertised/publicized?

Once approved by the IRB, advertisements for study will be placed in local newspapers and radio stations. Additionally, prospective participants are recruited by word of mouth and through liaison to other local clinical services.

Do you have ads/recruitment material requiring review at this time?

No

Does this study involve a clinical trial?

Yes

YOU MUST REGISTER AT [ClinicalTrials.gov](http://ClinicalTrials.gov) IMMEDIATELY UPON RECEIPT OF IRB APPROVAL AND **PRIOR TO ENROLLMENT** OF THE FIRST SUBJECT. YOU WILL BE PROVIDED WITH A NCT REGISTRATION NUMBER ON REGISTRATION. PLEASE REVISE THIS SECTION OF THE PROTOCOL SUMMARY FORM TO INCLUDE THE NCT NUMBER AND RE-SUBMIT AS AN AMENDMENT TO THE IRB.

### Concurrent Research Studies

Will subjects in this study participate in or be recruited from other studies?

Yes

Describe concurrent research involvement

All patients will be seen by one of our psychiatrists or psychologists for a screening evaluation and mental status examination as part of routine admission procedures at STARS as part of protocol #6582R, PI: [name]; Evaluation of Potential Substance Abuse Participants.

### Inclusion/Exclusion Criteria

Name the subject group/sub sample

All participants

Create or insert table to describe the inclusion criteria and methods to ascertain them

1. Individuals between the ages of 18-60  
(Clinical interview)

2. Meets DSM-5 criteria of current opioid use disorder present for at least six months, supported by a positive urine for **opioids**

---

( MINI interview by therapist, Clinical interview with psychiatrist, DSM-5 criteria review, and urine toxicology)

3. Seeking treatment for opioid use disorder

( Participant self-report, MINI interview by therapist, Clinical interview by psychiatrist)

4. Capable of giving informed consent and complying with study procedures

( Clinical interview by psychiatrist)

5. Not underweight; defined as  $BMI \geq 18.5$

( Calculation of BMI using weight and height of participant)

Create or insert table to describe the exclusion criteria and methods to ascertain them

1. Lifetime history of DSM-5 diagnosis of schizophrenia, schizoaffective disorder, or bipolar disorder

(MINI interview by therapist, Clinical interview by psychiatrist)

2. Current DSM-5 criteria for any other psychiatric disorder that in the investigator's judgment is unstable, would be disrupted by the study medication, or is likely to require pharmacotherapy or psychotherapy during the study period. Concurrent treatment with other psychotropic medication is exclusionary.

( MINI interview by therapist, Clinical interview and mental status exam by psychiatrist, contact with collateral information as needed and available)

3. Individuals who meet DSM-5 criteria for any substance use disorders - severe, other than opioid and nicotine use disorder. Physiological dependence on alcohol or sedative-hypnotics is exclusionary.

(MINI interview by therapist, Clinical interview by psychiatrist)

4. A recent history of binge-use of alcohol or sedative-hypnotics (using large amounts in a short time to severe intoxication or blackouts).

(Clinical interview by psychiatrist)

5. Pregnancy, lactation, or failure to use adequate contraceptive method in female patients who are currently engaging in sexual activity with men.

( Clinical interview by psychiatrist, physical examination and medical history by psychiatrist or NP, urine pregnancy test, serum HCG)

6. Unstable medical conditions, such as AIDS, cancer, uncontrolled hypertension (blood pressure  $> 140/90$ ), uncontrolled diabetes, pulmonary hypertension or heart disease.

(Medical history and physical examination by psychiatrist or NP, laboratory tests (serum Chem-20 and CBC, urinalysis), ECG)

7. Legally mandated to participate in a substance use disorder treatment program.

( Participant self-report, Clinical interview by psychiatrist)

8. Current or recent history of significant violent or suicidal behavior, risk for suicide or homicide **(MINI interview by therapist, Clinical interview by psychiatrist)**

9. Currently meets DSM-5 diagnosis for an eating disorder with low body weight (BMI <20)  
( MINI interview by therapist, Clinical interview by psychiatrist)

10. History of accidental opioid overdose in the last three years or any other significant history of overdose following detoxification within past 10 years defined as an episode of opioid-induced unconsciousness, whether or not medical treatment was sought or received.  
( MINI interview by therapist, Clinical interview by psychiatrist)

11. Elevated liver function tests (AST and ALT > 3 times the upper limit of normal) or impaired renal function (GFR<60 ml/min)  
( Laboratory tests -serum Chem-20)

12. Known history of allergy, intolerance, or hypersensitivity to lorcaserin, naltrexone or any other study medications  
( Participant self-report, Clinical interview by psychiatrist)

13. Concurrent use of migraine medications containing ergotamine (Cafergot, Ergomar) or dihydroergotamine (Migranal), 5HT2B receptor agonists like cabergoline, or medications metabolized by CYP2D6 (thioridazine, tamoxifen, metoprolol, aripiprazole, codeine)  
( Clinical interview by psychiatrist)

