**Side Effects of Naltrexone:** Naltrexone has been associated with reversible hepatocellular injury indicated by elevated liver enzymes when administered at doses substantially greater than the 50mg per day dose recommended for maintenance treatment of opiate dependence and proposed for the present studies. When used in the recommended dose range in opiate-dependent patients, this risk is remote (Brahen et al., 1988). Naltrexone is therefore contraindicated in patients with acute hepatitis or liver failure, and such patients are excluded from the study. Patients with hepatic enzyme levels greater than 3 times the upper limit of normal are therefore excluded. XR-naltrexone achieves higher blood levels than oral naltrexone initially, but these should remain lower than levels associated with hepatitis. If naltrexone-induced hepatitis were to occur during treatment with naltrexone injections, where the naltrexone would be only very slowly eliminated, this would prolong exposure to the offending agent. However, the experience with long-acting injectable naltrexone also suggests it is safe. In our studies with long-acting naltrexone several patients experienced elevation in liver enzymes, which were determined to be related to hepatitis C. One patient in the XR-naltrexone trial developed diabetes mellitus, which was deemed unlikely to be study related.

During the outpatient detoxification phase of the study, patients will have daily doses of oral naltrexone supervised at STARS. If a patient misses one or more oral naltrexone doses and resumes regular opiate use, then taking a dose of naltrexone will precipitate opiate withdrawal, which may be quite severe. Patients will be warned not to take the naltrexone if they have missed their dose for more than three days in a row and resumed opiate use for more than one day. Patients will be advised to report to STARS for clinical assessment by a study physician. If history and urine toxicology findings suggest a lapse or possible relapse, a naloxone challenge may be necessary. If the naloxone challenge is positive (withdrawal is precipitated), then the patient will be managed according to guidelines described above (see section entitled Handling of Lapses and Relapses). Relapsed patients who cannot resume naltrexone are referred for inpatient detoxification or outpatient buprenorphine or methadone maintenance.

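### Exclusion 11 joins AST and ALT with *and*, so read literally it leaves a person with only one raised enzyme eligible; it should say *or*

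*Protocol*

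**What the plan says.** The liver limit appears in two places in the Protocol.

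- **Inclusion/Exclusion Criteria, exclusion 11.** The criterion concerns elevated liver function tests, with the limit in parentheses: "AST and ALT > 3 times the upper limit of normal". The same line continues "or impaired renal function (GFR<60 ml/min". The only method listed for checking it is the serum chemistry panel.
- **Potential Risks, Side Effects of Naltrexone.** After stating that acute hepatitis and liver failure are contraindications and grounds for exclusion, the text says: "Patients with hepatic enzyme levels greater than 3 times the upper limit of normal are therefore excluded". It names no enzyme and does not ask for both to be raised.

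The Potential Risks text also puts the hazard in proportion. On oral naltrexone it says: "When used in the recommended dose range in opiate-dependent patients, this risk is remote". On the depot form it says: "However, the experience with long-acting injectable naltrexone also suggests it is safe". It notes too that if hepatitis did occur after an injection, slow elimination would lengthen the exposure.

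Under Recruitment Procedures, staff training includes "weekly discussion of inclusion/exclusion criteria and study eligibility for each screening participant".

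**The concern.** The eligibility table is what staff apply when they decide whether a candidate may enter. Its liver line can be read as requiring two raised enzymes before anyone is excluded, while the risk section, which gives the reason for the limit, contains no such requirement. A screener who follows the table to the letter could admit a person with one enzyme well above the limit.

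What is at stake is participant safety. Every participant, in either arm, is offered open-label depot naltrexone, which cannot be withdrawn once injected. The screening result therefore carries weight. Blood and other Biological Samples schedules blood chemistry only at screening and Week 7, whereas the Lay Summary places the injections at the end of week 1 and at week 5. The discontinuation criteria mention monthly serum tests, so an interim check is possible, but a monthly test need not fall before the first injection.

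**Working it through.** No figure in the plan depends on this criterion, so there is no calculation to reproduce. The check is to set the two texts side by side and work through the logic.

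**Inputs**

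- Exclusion 11: both enzymes named, joined by *and*, threshold three times ULN.
- Side Effects of Naltrexone: hepatic enzyme levels in general, same threshold, no statement that both are needed.

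**Outcome by screening pattern**

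| Above the limit | Exclusion 11, literal | Exclusion 11, read as a list of tests | Risk section, natural reading |
|---|---|---|---|
| Neither | eligible | eligible | eligible |
| AST only | eligible | excluded | excluded |
| ALT only | eligible | excluded | excluded |
| Both | excluded | excluded | excluded |

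The literal wording excludes 1 of the 3 patterns with any elevation; the natural reading of the risk section excludes 3 of 3. They differ on 2 of the 4 patterns. This count describes the rule and not the risk, because the patterns are not equally likely.

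**Hypothetical case.** Take a candidate with ALT at 4 times and AST at 2 times ULN. Under literal exclusion 11 the condition *AST above 3 and ALT above 3* is false, so the candidate is eligible. Under the natural reading of the risk section a hepatic enzyme exceeds 3 times ULN, so the candidate is excluded. With *or* in exclusion 11, both places exclude.

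**How many people.** The expected number would be 60 planned participants times the share of otherwise eligible candidates with an isolated elevation. The documents do not give that share. The nearest statement, about the group's own studies of long-acting naltrexone, is that "several patients experienced elevation in liver enzymes, which were determined to be related to hepatitis C"; it gives no count, denominator, level or AST/ALT split. The product is therefore left uncomputed.

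**Effect on the comparison.** Liver tests belong to the screening work-up, before randomisation, and the criterion is the same for both arms. The SAP analyses all randomised participants. Either wording changes who may enter, but neither favours one arm.

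**The case against.** The strongest reply is that exclusion 11 has an ordinary reading with no defect. The criterion is elevated liver function tests, and the parenthesis names the two tests and the limit that each must meet. An investigator may well read it that way, and the two places then agree. The *or* that follows does not settle the matter: it stands outside the parenthesis and joins two separate organ criteria, so it says little about *and* inside a list of tests.

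The risk section is also less explicit than it first looks. A reader might infer that it expressly excludes isolated elevations, and that the Protocol therefore contradicts itself. The text does not support that: it uses a plural, names no enzyme and never mentions one raised without the other. The mismatch is one of natural reading.

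Other safeguards exist. Acute hepatitis and liver failure are excluded separately; exclusion 6 bars unstable medical conditions through an open-ended list; and a single trained clinic team reviews each candidate's eligibility weekly.

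All of this stands as a limit on severity. It does not remove the ambiguity. Exclusion 6 does not name liver disease. The weekly review works from the same criteria, so it is not fully independent of their wording. Exclusion 11 lists a laboratory panel as its only method, which invites direct comparison of values with the written rule. Finally, the Protocol gives no reason for wanting both enzymes raised, so nothing speaks for the literal reading as the intended one.

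**Conclusion.** The point holds as a minor safety-wording defect. Taken literally, exclusion 11 is looser than the natural reading and stated purpose of the liver limit elsewhere in the Protocol, and the gap is exactly the person with one enzyme above the limit.

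The conclusion rests on two judgements: that some staff could read *and* as requiring both, and that the risk section means any hepatic enzyme above the limit. Both are reasonable, but neither is stated in the text.

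A reader might go further and infer that unsuitable people will be enrolled, or that the trial has a material hepatic safety gap. The documents do not support this. They show no enrolment error, describe the hepatic risk as remote at recommended doses, and give no basis for estimating how many people would be affected. The treatment comparison is not biased.

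**What to change.** In exclusion 11, replace *and* with *or* between the enzymes, so that AST or ALT above three times ULN excludes. The threshold, the renal limit and the screening tests stay as they are. The criterion then matches the natural reading of the risk section.

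The cost is one word in the eligibility table and possibly a few more screen failures, namely people with an isolated elevation who would otherwise have entered on the literal reading. No change to the SAP is needed.

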### Potential Risks

**Study Medication Risks:** One of the main risks associated with participation is drug administration. Lorcaserin (or Belviq©) was approved by the FDA for treating obesity, is generally well tolerated, and has low abuse potential, though it is a schedule IV substance. The target daily dose of lorcaserin in the proposed study (20 mg) is the current FDA approved dose for the treatment of weight management. In clinical trials, headache was the only reported side effect to occur at a frequency much greater than placebo. Other possible side effects of lorcaserin include: constipation, dry mouth, headache, nausea, and dizziness. Some rare but serious side effects include hypoglycemia in patients with Type 2 diabetes, serotonin syndrome, agitation, confusion, hallucinations, arrhythmias, cardiac valve disease, depression, thoughts of suicide, and an erection lasting longer than 4 hours.

The combination of lorcaserin with other serotonergic medications (e.g., 5HT3 antagonist antiemetics, bupropion, triptans, SSRIs, SNRIs, TCAs, St. John's Wart, tryptophan), medications that impair the metabolism of serotonin (e.g., MAO inhibitors, dextromethorphan, tramadol, lithium), or antidopaminergic medications (e.g., antipsychotics) may enhance serotonergic effects, and this could result in rare but serious serotonin syndrome reaction. Signs of serotonin syndrome include: mental

status changes (e.g., anxiety, agitated delirium, restlessness, and disorientation); easy startle, autonomic manifestations (e.g., diaphoresis, tachycardia, hyperthermia, hypertension, vomiting, and diarrhea); and neuromuscular hyperactivity (e.g., tremor, muscle rigidity, myoclonus, hyperreflexia, and bilateral Babinski sign).

The combination of lorcaserin with ergot derivatives is contraindicated. The use of these drugs together may increase the risk of developing valvular heart disease in addition to enhancing serotonergic effects that may result in serotonin syndrome. The combination of lorcaserin with 5HT2B-R agonists (e.g., cabergoline) is contraindicated due to the increased risk of cardiac valvulopathy. Lorcaserin is a moderate CYP2D6 inhibitor and may decrease the clearance of drugs metabolized by CYP2D6, and thus raise these other drug levels increasing the risk of toxicity. Lorcaserin is contraindicated in pregnancy due to the fact that weight loss offers no clinical benefit in pregnancy and is advised against.

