### **1) Screening Procedures**

In order to minimize the risk associated with the study, subjects undergo a comprehensive medical and psychiatric evaluation during the screening procedure. The baseline medical evaluation consists of a physical examination, blood chemistry profile (including liver function tests), complete blood count, urinalysis, serum pregnancy test, urine toxicology and is designed, along with the clinical history, to detect chronic and/or unstable medical illnesses. A comprehensive psychiatric assessment is performed during the screening process, and is intended to detect and assess all past and current psychiatric disorders. The eligibility criteria (see above) are designed to minimize the medical and psychiatric risks to participants by excluding those for whom participation would place them at an increased risk. Special attention will be given to patient's concurrent use of medications. Participants on medications that meet exclusion criteria will not be included in the study. If participants have recently completed another study at STARS, we will ensure, as with other medications, that there are no drug-drug interactions with the possible recent exposure to other study medications or will ensure proper time for wash-out between studies.

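### The protocol warns that lorcaserin with triptans, 5HT3 antagonist antiemetics or tryptophan could cause serotonin syndrome, but no exclusion names these drugs and no rule prohibits them during dosing

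*Protocol*

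**What the plan says.** **The warning.** Potential Risks (Study Medication Risks) begins "The combination of lorcaserin with other serotonergic medications (e.g., 5HT3 antagonist antiemetics, bupropion, triptans, SSRIs" and, after further antidepressants and a herbal product, continues "tryptophan), medications that impair the metabolism of serotonin (e.g., MAO inhibitors, dextromethorphan, tramadol, lithium". It adds drugs that block dopamine and gives serotonin syndrome as the possible result.

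**The drug exclusions.** Two criteria under Inclusion/Exclusion Criteria deal with concurrent medication. Exclusion 2 ends: "Concurrent treatment with other psychotropic medication is exclusionary". The term psychotropic is not defined. Exclusion 13 reads "Concurrent use of migraine medications containing ergotamine (Cafergot, Ergomar) or dihydroergotamine (Migranal), 5HT2B receptor agonists like cabergoline, or medications metabolized by CYP2D6" and then gives five drug names in brackets.

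**Screening.** Recruitment Procedures provides for "weekly discussion of inclusion/exclusion criteria and study eligibility for each screening participant". Screening Procedures promises particular care over concurrent medication and states "Participants on medications that meet exclusion criteria will not be included in the study". On people who recently finished another study at the clinic, it says staff will make sure there are no drug interactions, and that this is also what is done for other medicines.

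**After entry.** The section on minimizing risks (Study Procedures) provides for psychiatrist counselling during consent on lorcaserin alone and in combination, monitoring for serotonin syndrome, and an on-call physician at all hours. Serotonin syndrome is an example under the medical drop-out criterion in Study Discontinuation. Assessment Instruments lists a weekly Concomitant Medications Form. The plan has no list of prohibited medication for the dosing period.

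**The concern.** The safety section and the eligibility criteria do not match. The protocol names specific drugs as hazardous with lorcaserin, yet a screener working from the written criteria finds no mention of three of them. The closest match is telling: exclusion 13 addresses migraine treatment but stops at ergot products, so a triptan user does not meet it.

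What is at stake is participant safety. Recognising serotonin syndrome may be harder in this setting than usual. The protocol's account of opioid withdrawal (agitation, raised pulse and blood pressure, at times confusion) overlaps with its account of serotonin syndrome (agitated delirium, tachycardia, hypertension, disorientation). Preventing the combination is therefore more dependable than detecting its effects. The need for such drugs is also foreseeable, because the protocol lists headache and nausea among lorcaserin's side effects and expects nausea in withdrawal.

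**Working it through.** No formula applies and the plan gives no figure to reproduce. The check compares the warning with the exclusions, and then with the other safeguards.

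**Step 1. Each entry in the warning against the exclusions.**

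| Entry in the warning | Exclusion 2 (psychotropics) | Exclusion 13 | Result |
|---|---|---|---|
| Triptans | Not named; not plainly psychotropic | Migraine drugs limited to ergots | Named in 0 of 13 exclusions |
| 5HT3 antagonist antiemetics | Not named; not plainly psychotropic | Not named | Named in 0 of 13 |
| Tryptophan | Not named; only a very broad reading would reach it | Not named | Named in 0 of 13 |
| Tramadol, dextromethorphan | Not named; a broad reading might reach them | Covered only if the CYP2D6 class is open and includes them | Cannot be settled from the documents |
| SSRIs, SNRIs, TCAs, bupropion, MAO inhibitors, lithium, antipsychotics | Reasonably covered as a class | Not needed | Treated here as barred at entry |

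The herbal product in the warning also turns on how psychotropic is read, and it is not counted. The tally is 3 entries named in no exclusion and 2 that depend on interpretation. The warning's lists are given as examples, so a share of a total would mean nothing.

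**Step 2. The CYP2D6 wording.** Exclusion 13 bars "medications metabolized by CYP2D6 (thioridazine, tamoxifen, metoprolol, aripiprazole, codeine", with nothing to mark the five names as examples. Potential Risks, however, gives a reason that applies to the whole class: "Lorcaserin is a moderate CYP2D6 inhibitor and may decrease the clearance of drugs metabolized by CYP2D6". An open class is the more natural reading. The documents do not say whether tramadol or dextromethorphan belongs to it.

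**Step 3. Does a rule explain the difference?** One candidate is that contraindicated drugs are excluded and cautioned drugs are monitored. Ergots and 5HT2B agonists are called contraindicated and are excluded, which fits. CYP2D6 drugs are only cautioned and are excluded all the same. The serotonergic drugs are also only cautioned, with a serious outcome named, and are not excluded as a group. The plan does not explain the difference.

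**Step 4. Safeguards before exposure.** The weekly eligibility discussion works from the written criteria, which omit the three entries. The screening interaction check and the consent counselling go beyond those criteria, and either could pick up a triptan user. Neither names these drugs or says that using them prevents entry.

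**Step 5. Safeguards during dosing.** Visits are daily during detoxification and induction, and a physician is present throughout the induction procedure. In weeks 2-7 there are 2 visits a week, which leaves 7 − 2 = 5 days without one, though on-call cover continues. The medication form records what is taken, but no rule says which entries on it are not allowed.

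**Step 6. Antidepressants on study.** Exclusion 2 keeps antidepressants out at entry. The Evaluation of Depression paragraph allows one to be started later, and does not say whether lorcaserin or placebo then continues. A prohibited list that ignored this route would be uneven.

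**The case against.** The strongest reply is that the plan manages these combinations by clinical judgement. The word contraindicated is kept for ergots and 5HT2B agonists, and both are excluded. The serotonergic warning is conditional and calls the reaction rare. CYP2D6 drugs have their own rationale: slower clearance, higher levels and toxicity. The monitoring text expects some participants to be on other medicines. At most about 40 people are planned to receive lorcaserin. The consent form is not part of the text reviewed, so what participants are told to avoid is not visible.

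Much of this stands. It rules out several stronger conclusions that a reader might draw:

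- *That screening removes only people who meet a listed exclusion, so users of these drugs pass straight through.* The Screening Procedures text also describes an interaction check for other medicines, and drugs that the protocol itself lists as interacting with lorcaserin fall naturally within it.
- *That every safeguard acts only after exposure.* The combination-risk counselling takes place during consent.
- *That participants lack medical cover on five days a week.* Those are days without a visit; a physician is on call around the clock.
- *That tramadol and dextromethorphan are shown to be left out.* Exclusion 13 most naturally reads as an open class, and exclusion 2 might also reach them.

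What remains is narrow. A brief interaction check that names no drug, followed by counselling and monitoring, leaves the decision to whoever is screening. Case-by-case handling may be deliberate, but the plan neither says so nor says how these drugs should be handled.

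**Conclusion.** The point holds in a limited form. Triptans, 5HT3 antagonist antiemetics and tryptophan are in the protocol's own serotonin-syndrome warning, are named in none of the 13 exclusions, and are not prohibited during dosing. The other safeguards reduce the risk but do not expressly bar them. Tramadol and dextromethorphan need clarification only.

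This rests on two assumptions: that psychotropic in exclusion 2 does not plainly cover the three entries (least certain for tryptophan), and that no prohibition sits in material not available for review. The documents do not give the number of users, so the size of the risk cannot be estimated.

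This is a modest safety improvement worth making. A reader might take a safety gap of this kind to undermine the comparison of arms. It does not: the point depends on no sample size, power or error rate and leaves the planned analyses unchanged.

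**What to change.** - **Exclusion 13, entry.** Add current or as-needed use of triptans, 5HT3 antagonist antiemetics and tryptophan. The as-needed wording matters because some of these may be taken only now and then.
- **Exclusion 13, clarity.** State that the five bracketed CYP2D6 names are examples, and name dextromethorphan and prescribed tramadol. Limiting tramadol to prescribed use keeps the opioid disorder under treatment from becoming an exclusion.
- **Dosing period.** Prohibit the same drugs while lorcaserin or placebo is taken, and check for them on the weekly Concomitant Medications Form.
- **Consistency.** If an antidepressant named in the warning is started under Evaluation of Depression, stop lorcaserin or placebo first.

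The cost is a short amendment to one criterion, a line on prohibited medication, a sentence on antidepressants, and a check on a form already in use. The downsides are possibly a few more screen failures, a slightly later start for some, and early stopping of study drug in anyone who begins such an antidepressant. Those participants stay in the analysis, because the SAP analyses all randomized participants by intention to treat.
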